2.1 Data analysis general information

The data will be analyzed by Novartis and/or by the designated CRO. It is planned that the data from all centers that participate in this protocol will be used for analysis. Analysis datasets and statistical outputs will be produced using the most recent SAS® Version 9.4 (SAS Institute Inc., Cary, NC, USA), and stored in Novartis global programming & statistical environment (GPS).

As the primary endpoint analysis will be performed at Week 12, there will be a database freeze after all patients have completed Week 12 assessments. A selected Novartis clinical team will be unblinded to the Week 12 results. Summary results may be shared internally and externally; however, individual unblinded patient data will not be disclosed. A final database lock will occur when all patients have completed the study.

Summary statistics for continuous variables will include number of patients (N), mean, standard deviation, minimum, lower quartile, median, upper quartile, maximum. Summary statistics for discrete variables will be presented in the number and percent of patients in each category. Summary statistics will also be presented graphically wherever applicable.

If not otherwise specified, p-values and confidence interval (CI) will be presented as two-sided. Unless otherwise stated, the default level of significance will be set to 5% (two-sided, family-wise type-I-error).

Data analyses will be presented by treatment group. Efficacy and safety data for the placebo-controlled period (or the entire treatment period as appropriate) will be presented by the following 3 treatment groups. Patients may be included in more than one treatment group for some analyses (e.g. exposure-adjusted adverse events over the entire treatment period).

Eligible patients will be randomized to secukinumab 150 mg (Group 1), secukinumab 300 mg (Group 2) or placebo (Group 3) for the first 12 weeks. Note that the treatment groups for a patient may differ depending on the time period of the analysis and whether one assesses the patient for efficacy or safety.

The analysis will be conducted on all patients' data at Week 12 and at the time, the trial ends (Week 52).

Comparative efficacy data

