On-treatment period: The period where the patients are exposed to the study treatment. For this study, the treatment phase consists of 52 weeks. For this study, the treatment phase consists of 52 weeks (for treatment group 1 or group 2) for secukinumab, and 12 weeks of on-treatment period for placebo and 40 weeks of on treatment for secukinumab (for treatment group 3).

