2.8.1 Adverse events (AEs)

The crude rates of treatment emergent adverse events (i.e. events started after the first dose of study treatment or events present prior to the first dose of study treatment but increased in severity based on preferred term, and events until 12 weeks after last dose of study treatment) will be summarized by primary system organ class and preferred term.

In addition, exposure time-adjusted incidence rates including 95% confidence intervals will be provided for the entire treatment period to adjust for differences in exposure. A graphical display of the crude rates and exposure-adjusted incidence rates will be presented for all AEs and serious AEs by system organ class.

Adverse events will be summarized by presenting, for each treatment group, the number and percentage of patients having at least one AE, having an AE in each primary system organ class and having each individual AE (preferred term). Summaries (crude rates only) will also be presented for AEs by severity and for study treatment related AEs. If a particular AE 'severity' is missing, this variable will be listed as missing and treated as missing in summaries. If a subject reported more than one adverse event with the same preferred term, the adverse event with the greatest severity will be presented. If a subject reported more than one adverse event within the same primary system organ class, the subject will be counted only once with the greatest severity at the system organ class level, where applicable.

Separate summaries will be provided for

- adverse events suspected to be related to study drug by the investigator
- deaths
- serious adverse events
- adverse events leading to discontinuation
- adverse events leading to temporary dose interruption.
- adverse events of special interest

Adverse events will also be reported separately by SMQ according to MedDRA, using a narrow search. The MedDRA version used for reporting the study will be described in a footnote.

Follow-up period summaries will be done for all patients in follow-up.

A listing of non-treatment emergent adverse events will be done. These adverse events occurred before the first dose of the study treatment. The crude rates will be provided without treatment information.

For SAEs occurred during screening a listing will be prepared for all patients screened including screening failures.

Algorithms for date imputations will be provided in Programming Specifications.

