White blood cell Decreased	<LLN - 3.0 x 10e9 /L	<3.0 - 2.0 x 10e9 /L	<2.0 - 1.0 x 10e9 /L	<1.0 x 10e9 /L
Neutrophil count Decreased	<LLN - 1.5 x 10e9 /L	<1.5 - 1.0 x 10e9 /L	<1.0 - 0.5 x 10e9 /L	<0.5 x 10e9 /L
Lymphocyte count Decreased	<LLN - 0.8 x 10e9/L	<0.8 - 0.5 x 10e9 /L	<0.5 - 0.2 x 10e9 /L	<0.2 x 10e9 /L

		>1.5 - 3.0 x baseline;		
Creatinine increased*	>1 - 1.5 x baseline; >ULN - 1.5 x ULN	>1.5 - 3.0 xULN	>3.0 baseline; >3.0 - 6.0 x ULN	>6.0 x ULN
TBL increased	>ULN - 1.5 x ULN	>1.5 - 3.0 x ULN	>3.0 - 10.0 x ULN	>10.0 x ULN
GGT increased	>ULN - 2.5 x ULN	>2.5 - 5.0 x ULN	>5.0 - 20.0 x ULN	>20.0 x ULN
ALT increased	>ULN - 3.0 x ULN	>3.0 - 5.0 x ULN	>5.0 - 20.0 x ULN	>20.0 x ULN
AST increased	>ULN - 3.0 x ULN	>3.0 - 5.0 x ULN	>5.0 - 20.0 x ULN	>20.0 x ULN
ALP increased	>ULN - 2.5 x ULN	>2.5 - 5.0 x ULN	>5.0 - 20.0 x ULN	>20.0 x ULN
Glucose increased (Hyperglycemia)	>ULN - 8.9 mmol/L	>8.9 - 13.9 mmol/L	>13.9 - 27.8 mmol/L	>27.8 mmol/L
Glucose decreased (Hypoglycemia)	<LLN - 3.0 mmol/L	<3.0 - 2.2 mmol/L 7.75 - 10.34	<2.2 - 1.7 mmol/L	<1.7 mmol/L
Cholesterol high Hypertriglycerid emia	>ULN - 7.75 mmol/L 1.71 - 3.42 mmol/L	mmol/L >3.42 - 5.7mmol/L	>10.34 - 12.92 mmol/L >5.7 - 11.4 mmol/L	>12.92 mmol/L >11.4 mmol/L

*Note: for "creatinine increased" the baseline criteria do not apply

Shift tables will be presented comparing baseline laboratory result (CTCAE grade) with the worst results (expressed in CTCAE grade) during the treatment phase (either initial or entire) analyzed. Of note, baseline will be defined as last assessment prior to first dosing in initial treatment phase. Patients with abnormal laboratory values will be listed and values outside the normal ranges will be flagged.

Summaries for newly occurring or worsening clinically notable lipid abnormalities will also be provided cumulatively for each of the following parameters and categories:

- HDL:
 - <=LLN
 - <0.8 x LLN
- LDL, cholesterol, triglycerides:
 - >=ULN
 - >1.5 x ULN
 - >2.5 x ULN

Newly occurring or worsening liver enzyme abnormalities will also be summarized based on the event criteria given in Table 2.8-3 below:

Table 2.8-2 Liver-related events

Parameter	Criterion
ALT	>3xULN; >5xULN; >8xULN; >10xULN, >20xULN
AST	>3xULN; >5xULN; >8xULN >10xULN; >20xULN
ALT or AST	>3xULN; >5xULN; >8xULN >10xULN; >20xULN
TBL	>1.5xULN, >2xULN, >3xULN,

ALP	>2xULN, >3xULN, >5xULN

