2.8.4.2 Vital signs

Analysis in vital signs measurement using descriptive summary statistics for the change from baseline for each post-baseline visit will be performed. These descriptive summaries will be presented by vital sign and treatment group. Change from baseline will only be summarized for patients with both baseline and post-baseline values and will be calculated as:

$$\text{change from baseline} = \text{post-baseline value} - \text{baseline value}$$

The number and percentage of patients with newly occurring notable vital signs will be presented. Criteria for notable vital sign abnormalities are provided in Table 2.8-4 below.

Table 2.8-3 Criteria for notable vital sign abnormalities

Vital sign (unit)	Notable abnormalities
Systolic blood pressure (mmHg)	$\geq 140 \text{ mmHg}$ or $< 90 \text{ mmHg}$
Diastolic blood pressure (mmHg)	$\geq 90 \text{ mmHg}$ or $< 60 \text{ mmHg}$
Pulse (bpm)	$> 100 \text{ bpm}$ or $< 60 \text{ bpm}$

An overview of the safety analyses is described in Table 2.8-1 below.

Table 2.8-4 Overview of analyses on some safety endpoints

Analysis period	SAEs	AEs	Study drug related AEs	AESI	Notables for vitals/ECG/lab criteria
Day 1 – Week 12	
 • Crude rates • Exposure time adjusted incidence rates* 	
 • Crude rates • Exposure time adjusted incidence rates* 	
 • Crude rates 	
 • Crude rates • Exposure time adjusted incidence rates* 	
 • Crude rates
Entire Treatment (upto Week 52)	
 • Crude rates • Exposure time adjusted incidence rates* 	
 • Crude rates • Exposure time adjusted incidence rates* 	
 • Crude rates 	
 • Crude rates • Exposure time adjusted incidence rates* 	
 • Crude rates

*Exposure time adjusted incidence rates will be done for the following:

- at the PSOC level for all SAEs and all AEs
- at the preferred term level for
 - all SAEs and AESIs

- the common AEs, which are defined as at least 2% of the patients in the combined AIN457 groups during the initial treatment period or events that had an incidence rate of at least 5.0 cases per 100 subject-years in the combined AIN457 groups during the entire treatment period

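### Summaries to Week 52 of AE severity, drug-related AEs and notable lab, vital-sign and ECG findings use crude rates only, although time on placebo is 12 weeks and time on secukinumab 40 to 52 weeks

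*SAP*

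**What the plan says.** Section 2.8.1 plans exposure-adjusted incidence rates for the entire treatment period, expressly because exposure differs. For two categories it then stops at crude rates: "Summaries (crude rates only) will also be presented for AEs by severity and for study treatment related AEs".

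Table 2.8-4 (section 2.8.4.2) has two rows, Day 1 to Week 12 and "Entire Treatment (upto Week 52"). In both rows, drug-related AEs and notable vital-sign, ECG and laboratory findings have crude rates only. SAEs, AEs and AESIs have crude and exposure-adjusted rates. AEs by severity have no column. The footnote limits the adjusted rates to all SAEs and AEs by primary system organ class, and to SAEs, AESIs and common AEs by preferred term.

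On treated time, section 2.1.1 says that "the treatment phase consists of 52 weeks (for treatment group 1 or group 2) for secukinumab", and for the group first given placebo it sets "12 weeks of on-treatment period for placebo and 40 weeks of on treatment for secukinumab (for treatment group 3"). Section 5.4.1 defines crude incidence as the number of patients with the event divided by the number of patients, with no term for time.

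On columns, section 2.1 says: "Efficacy and safety data for the placebo-controlled period (or the entire treatment period as appropriate) will be presented by the following 3 treatment groups". It adds: "Patients may be included in more than one treatment group for some analyses (e.g. exposure-adjusted adverse events over the entire treatment period").

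**The concern.** Every placebo patient moves to secukinumab at Week 12. A crude percentage to Week 52 therefore reflects how long a patient was observed on a treatment as well as the risk on it. The SAP sees this for AEs in general and corrects for it, but not for these three categories, and it gives no reason for the difference.

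The categories are not marginal. The safety objective in Table 1.2-1 is framed as the frequency and severity of AEs and changes in laboratory, vital-sign and ECG values. A table to Week 52 with a placebo column beside two dose columns will be read as a comparison, even with no test attached. Within a dose it may also mix patients with 40 and 52 weeks of treatment.

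**Working it through.** **Inputs.** Treated time is 12 weeks on placebo, 40 weeks on secukinumab after the switch and 52 weeks for patients randomised to secukinumab (section 2.1.1). There are 165 patients per group, and placebo patients are re-randomised 1:1 at Week 12 (section 1.1), so each dose gains about 82.5 switchers. The SAP gives no event rates, so a range of 12-week risks *r* is assumed.

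**The plan's own figures.** The SAP states no figure for the distortion. Its time figures are consistent: 12 + 40 = 52 weeks. The exposure example in section 5.4.3 also works: an event on day 110 after 100 days of placebo counts 110 − 100 = 10 days on the second treatment. That example moves the later event to secukinumab, but it concerns exposure-adjusted rates, not crude tables.

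**Layout A: the placebo column stops at Week 12 and later events of switchers count under their dose.** Assume equal risk on drug and placebo, constant hazard and full follow-up. Crude risk over T weeks is 1 − (1 − r)^(T/12), and the apparent ratio is that value divided by *r*. The dose column weights 52-week and 40-week patients 165 : 82.5.

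| 12-week risk | 40 weeks (ratio) | 52 weeks (ratio) | Dose column (ratio) |
|---|---|---|---|
| 1% | 3.3% (3.29) | 4.3% (4.26) | 3.9% (3.94) |
| 5% | 15.7% (3.14) | 19.9% (3.99) | 18.5% (3.71) |
| 10% | 29.6% (2.96) | 36.7% (3.67) | 34.3% (3.43) |
| 20% | 52.5% (2.62) | 62.0% (3.10) | 58.8% (2.94) |
| 30% | 69.5% (2.32) | 78.7% (2.62) | 75.6% (2.52) |
| 50% | 90.1% (1.80) | 95.0% (1.90) | 93.4% (1.87) |

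The limits for rare events are the ratios of time: 40/12 = 3.33, 52/12 = 4.33, and for the dose column (165 × 52 + 82.5 × 40)/247.5 = 48 weeks, so 48/12 = 4.0. The ratio falls below 3 once the 12-week risk exceeds about 9% (40 weeks), 22% (52 weeks) or 19% (dose column).

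**Findings detected at visits.** Laboratory, vital-sign and ECG abnormalities are seen only when measured. Table 2-1 has six post-baseline visits to Week 12 (Weeks 1, 2, 3, 4, 8, 12) and six later (Weeks 16, 24, 32, 40, 48, 52). If a parameter is measured at every visit, with a constant small probability per visit, the ratios are 6/6 = 1.0 for switchers and 12/6 = 2.0 for patients randomised to secukinumab. For the dose column, (165 × 12 + 82.5 × 6)/247.5 = 10 visits, so 10/6 = 1.67.

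**Layout B: switchers stay under placebo.** Every column then has 52 planned weeks and the ratios above vanish. But 40 of the 52 weeks in the placebo column, or 77%, are secukinumab time.

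**With exposure adjustment.** The rate in section 5.4.3 is patients with an event divided by time at risk. Under the Layout A assumptions its ratio is 1.0 by construction. For example, a 12-week risk of 5% is 22.3 per 100 patient-years in every column. Crude rates over Day 1 to Week 12 also give 1.0, because planned time is equal.

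**The case against.** The strongest reply is that the like-for-like comparison is already planned. Table 2.8-4 has a Day 1 to Week 12 row with crude rates for drug-related AEs and notables. This stands for those two categories. It does not cover severity, which has no column, and section 2.8 says only that summaries by period may be done separately.

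It can also be said that the tables are descriptive, that the main AE, SAE and AESI summaries are exposure-adjusted, and that AESIs get Kaplan-Meier estimates. All of that is correct. It limits the harm but does not make the Week 52 crude rows interpretable.

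A reader might infer that every one of these summaries will show a three- to fourfold excess on secukinumab. The documents do not support that. The multiplier needs Layout A, which the SAP does not state for crude tables. Section 2.1 lets patients appear in more than one group only for some analyses, and section 2.8 says that treatment received differs from treatment assigned only if the wrong treatment was given throughout, which points towards Layout B. The multiplier also needs uncommon events, and it fits findings detected at visits poorly.

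A reader might also infer that abnormalities arising on placebo will be counted as new on secukinumab, since section 2.8.3 says: "Of note, baseline will be defined as last assessment prior to first dosing in initial treatment phase". That sentence belongs to the CTCAE shift tables, and the consequence depends on the same unstated layout. It is possible, not established.

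**Conclusion.** The point holds in limited form. For AEs by severity, drug-related AEs and notable findings, the SAP applies a measure without time to periods of 12 against 40 to 52 weeks, and leaves out the adjustment that it makes elsewhere for that reason. The Week 52 display is hard to interpret under either layout.

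Under Layout A, with equal constant hazard and full follow-up, the apparent excess is about 3 to 4 times for AEs with a 12-week risk up to roughly 10-20%, and about 2 to 3 times or less above that. It may be under 2 times for notables if they are measured at every visit; the schedule for each parameter is not in this document. Under Layout B there is no such multiplier, but the placebo column is mostly secukinumab time.

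The primary and key secondary analyses and the main AE rates are not affected.

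**What to change.** - In section 2.8.1 and Table 2.8-4, add exposure-adjusted incidence rates for the entire period, by the method in section 5.4.3, for drug-related AEs, severe AEs and notable vital-sign, ECG and laboratory events.
- Confine crude comparisons with placebo to Day 1 to Week 12, and include AEs by severity there.
- Show Week 52 crude rates by the four treatment sequences defined in section 2.4.1, without a placebo contrast. This also settles the columns.
- If switchers' notable findings or shifts after Week 12 are shown under secukinumab, also show them against the last value before the first secukinumab dose.

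The adjusted rates assume a constant hazard and placebo time is all early, so they should be read with the Week 12 comparison and not in its place. The cost is SAP wording and a few more tables from data and methods already planned, with no effect on trial conduct.

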2.8.1.1 Adverse events of special interest (AESIs)

Safety topics of interest, such as risks defined in the Safety Profiling Plan (SPP), Risk Management Plan or topics of interest regarding signal detection or routine analysis are defined in the Program Case Retrieval Sheet that is stored in CREDI at the path Cabinets/CREDI Projects/A/AIN457A/Integrated Medical Safety.

To this end, the following events will be considered as adverse events of special interest:

- Major adverse cardiovascular events (MACE): identified per Novartis MedDRA Query (NMQ) “MACE (MI, Stroke, Cardiovascular death)”
- Inflammatory bowel disease: identified per NMQ “Inflammatory bowel disease”
- Infections and infestations: identified per SOC “Infections and infestations”
- Malignancy: identified per NMQ “Malignant or unspecified tumors (excluding BCC and SCC)”
- Hypersensitivity and injection site reaction: identified per SMQ “Hypersensitivity”

The crude rates and exposure-adjusted incidence rates for AESIs will be summarized. In addition, listings will be provided presenting which subjects experienced which risk.

Important note: For the evaluation of AESIs risks primary and secondary system organ classes of the MedDRA dictionary will be considered.

Adverse events of special interest analysis will be performed using the time to event analysis, the number of patients with an event, number of patients remaining at risk in the treatment group, estimate of the event rate and its estimated standard error, as estimable, will be provided for each treatment group. Median time to event and quartiles including 95% confidence intervals will be provided. The Kaplan-Meier estimates of the cumulative rate for each treatment group will be plotted.

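### The AESI covering hypersensitivity and injection site reactions is retrieved with a hypersensitivity query only, so some of the reactions it names may not be counted in it

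*SAP*

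**What the plan says.** SAP Section 2.8.1.1 lists five AESIs and ties each to a named search. The last reads "Hypersensitivity and injection site reaction: identified per SMQ", and the SMQ it names is Hypersensitivity. No second query follows.

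Three other statements bear on how the entry works:

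- The same section says that the safety topics of interest "are defined in the Program Case Retrieval Sheet that is stored in CREDI at the path" of an internal project folder. That sheet is not part of the SAP.
- The same section adds: "For the evaluation of AESIs risks primary and secondary system organ classes of the MedDRA dictionary will be considered".
- Section 2.8.1, on adverse events in general, says: "Adverse events will also be reported separately by SMQ according to MedDRA, using a narrow search". Section 2.8.1.1 gives no search scope of its own.

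On outputs, Section 2.8.1.1 states: "The crude rates and exposure-adjusted incidence rates for AESIs will be summarized". It also plans listings of affected subjects, a time-to-event analysis and Kaplan-Meier plots by treatment group. Table 2.8-4 and its footnote in Section 2.8.4.2 give every AESI exposure-adjusted rates at preferred-term level.

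**The concern.** The label promises two things and the rule defines one. A programmer who follows the rule runs the Hypersensitivity SMQ and puts the result under a heading that also names injection site reactions. Any local reaction coded to a term outside the SMQ drops out of that row without a trace. A reader of the study report, seeing the heading, could take the row as the injection-site rate.

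The topic matters in this trial. Every arm, placebo included, receives two syringes on each dosing day, and the sponsor itself chose injection site reaction as a topic of special interest. The AESI row is also the only place where the SAP sets up a grouped count that would include these reactions. The general tables count patients by system organ class and by single preferred term, so they do not show how many patients had any injection-site reaction.

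**Working it through.** The plan states no figure for this point, so the check is mainly a comparison of texts.

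**Step 1: label against named query (Section 2.8.1.1).**

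| AESI label | Named query | Does the query name cover the label? |
|---|---|---|
| Major adverse cardiovascular events | NMQ for MACE | Yes |
| Inflammatory bowel disease | NMQ of the same name | Yes |
| Infections and infestations ("Infections and infestations: identified per SOC" of the same name) | SOC | Yes |
| Malignancy | NMQ for malignant or unspecified tumors, without BCC and SCC | Broadly; the query name states its own limits |
| Hypersensitivity and injection site reaction | SMQ Hypersensitivity | First half only |

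Only in the fifth row does a harm named in the label have no search at all.

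**Step 2: is the missing half defined elsewhere?** The rest of the SAP contains no injection-site query, high-level term or preferred-term list. The note on primary and secondary system organ classes names no class for the fifth entry, so it adds no injection-site search.

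**Step 3: how much could be missed?** Let *s* be the share of patients with an injection-site reaction who have at least one such term inside the SMQ. The share missing from the AESI row is 1 − *s*. The SAP gives neither the SMQ's terms nor the mix of terms expected, so *s* may lie anywhere between 0 and 1. The share missed could be small if most reported terms are allergic in type and inside the SMQ, or nearly everything if most are non-allergic local terms outside it.

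**Step 4: what does a term lose by falling outside the AESI?** It loses the AESI listing, the time-to-event analysis and the Kaplan-Meier plot. It may also lose its exposure-adjusted rate at preferred-term level. Under Section 2.8.4.2, a non-serious term that is not an AESI gets that rate only if it is common. Common means at least 2% of the combined secukinumab groups in the initial period, or at least 5.0 cases per 100 subject-years in those groups over the entire period.

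- Planned secukinumab patients in the initial period: 2 × 165 = 330.
- 2% of 330 = 6.6, so at least 7 patients are needed (7/330 = 2.1%; 6/330 = 1.8%).
- A local term outside the SMQ seen in 6 or fewer patients initially gets no such rate unless it meets the second threshold. Reactions spread over several preferred terms could each fall below both.

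**Step 5: exposure to injections (Section 1.1).** Baseline and Weeks 1, 2, 3, 4 and 8 make 6 dosing days. Week 12 to Week 48 every 4 weeks makes (48 − 12)/4 + 1 = 10. At two syringes per day this is (6 + 10) × 2 = 32 injections per patient who completes dosing. This is context for the relevance of the topic; it says nothing about the size of any undercount.

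**The case against.** **Nothing is lost from safety reporting.** This stands. All treatment-emergent events are tabulated by system organ class and preferred term, with further summaries by severity and by relationship to study drug. Non-serious events above 2% have their own table, and exposure-adjusted rates by primary system organ class cover all events. The gap concerns the AESI outputs and the absent grouped count only.

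**The Case Retrieval Sheet may already hold the injection-site terms.** It may. But the SAP cites the sheet and then states its own rule. If the sheet adds such terms, the SAP states a different rule from the sheet. If it does not, half the label has no rule. The SAP entry needs correcting either way.

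**Labels in this list are shorthand, and the query is the operative rule.** The malignancy entry lends this some support, since its query leaves out two tumor types. It would be wrong to say that every other label matches its query exactly. But that query's name shows its limits, whereas here an entire named harm has no search.

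**One combined AESI is the sponsor's choice.** This also stands. Separate lines are preferable but not required to cure the defect.

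A reader might go further and infer that most injection-site reactions will be missing. The SAP does not support that, because it does not list the SMQ's terms. Putting a figure on it by assuming that 0-25% of reactions fall inside the SMQ only returns the assumption as a 75-100% undercount. Nor is narrow scope settled for this entry: the sentence in Section 2.8.1 concerns separate SMQ reporting and is not repeated for AESIs.

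**Conclusion.** The mismatch is real and rests on the SAP's text alone: the entry names two harms, its rule names a query for one, and no other rule fills the gap. Followed as written, it yields AESI rates, listings and time-to-event results labelled as covering injection site reactions but not defined to capture them. The size of the shortfall cannot be determined from the SAP and could run from little to nearly all, depending on the SMQ's content in the MedDRA version used, the scope applied and the terms reported. The documents do not support a claim that the reactions are mostly left out, or that they vanish from the report. No efficacy or confirmatory result is affected. The point should be corrected because the row can mislead and the repair is cheap.

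**What to change.** In Section 2.8.1.1:

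1. Add an explicit search for injection site reactions, for example the MedDRA high-level term or a preferred-term list. Preferably report it on its own AESI line beside the SMQ Hypersensitivity, with the same outputs as the other AESIs.
2. Note that a few terms may appear under both searches.
3. State whether the AESI SMQ is run with narrow or broad scope.
4. Make the entry agree with the Program Case Retrieval Sheet.

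If injection site reactions are not meant to be an AESI, remove them from the label instead.

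The cost is a wording change and at most one more search or AESI row per output, using adverse event terms already collected and coded. The only drawback is the small overlap between the two lines. Treatment, visits and the efficacy analyses do not change.
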